CTCAE	Common Terminology Criteria for Adverse Events
CTL	Clinical Trial Leader
CTM	Clinical Trial Manager
CTP	Clinical Trial Protocol
CTR	Clinical Trial Report
CYP450	Cytochrome P450

DDI	Drug-Drug Interactions
DILI	Drug Induced Liver Injury
DMC	Data Monitoring Committee
EC	Ethics Committee
ECG	Electrocardiogram
eCRF	Electronic Case Report Form
eDC	Electronic Data Capture
EMA	European Medicines Agency
EoT	End of Trial
EudraCT	European Union Drug Regulating Authorities Clinical Trials Database
FDA	The Food and Drug Administration
GEV	Gastroesophageal varices
GFR	Glomerular Filtration Rate
gMeans	Geometric Means
HA	Health Authority
HBV	Hepatitis B virus
HCV	Hepatitis C virus
HMG-CoA	3-Hydroxy-3-Methylglutaryl Coenzyme A
IB	Investigator's Brochure
ICH	International Conference on Harmonisation
IEC	Independent Ethics Committee
INR	International normalized ratio
IRB	Institutional Review Board
ISF	Investigator Site File
IUD	Intrauterine Device
IUS	Intrauterine Hormone-Releasing System
ITC	International Transporter Consortium's
K-EDTA	Potassium Ethylenediaminetetraacetic Acid
LC-MS/MS	liquid chromatography tandem mass spectrometry
LGL syndrome	Lown Ganong Levine syndrome
LPLT	Last patient last treatment
m1A	N ¹ –methyl adenosine
MATE	Multidrug and toxin extrusion protein

MATE1	Multidrug and toxin extrusion protein 1
MATE2-K	Multidrug and toxin extrusion protein 2-K
MedDRA	Medical Dictionary for Drug Regulatory Activities
MRE	Magnetic Resonance Elastography
MRP	Multidrug resistance-associated protein
MRP 2	Multidrug resistance-associated protein 2
MRP 3	Multidrug resistance-associated protein 3
NASH	Non-Alcoholic SteatoHepatitis
NMN	N ¹ -methylnicotinamide
OAT1	Organic anion transporter 3
OAT3	Organic anion transporter 3
OATP	Organic Anion Transporting Polypeptide
OATP1B1	Organic Anion Transporting Polypeptide 1B1
OATP1B3	Organic Anion Transporting Polypeptide 1B3
OCT	Organic Cation Transporter
OCT2	Organic Cation Transporter 2
OPU	Operative Unit
P-gp	P-glycoprotein
PK	Pharmacokinetics
PR	Pulse Rate
q.d.	quaque die (once a day)
RA	Regulatory Authority
REP	Residual effect period
RNA	Ribo-Nucleic Acid
SAE	Serious Adverse Event
SARS-CoV-2	Severe acute respiratory syndrome coronavirus 2
SC	Steering Committee
SLC	Solute Carrier Transporter Family
SMC	Safety Monitoring Committee
SmPC	Summary of Product Characteristics
SOP	Standard Operating Procedure
SUSAR	Suspected Unexpected Serious Adverse Reactions
t _{max}	Timepoint of maximum plasma concentration

TMF	Trial Master File
TSAP	Trial Statistical Analysis Plan
T2DM	Type 2 Diabetes Mellitus
$t_{1/2}$	Half lifetime
ULN	Upper limit of normal
WHO	World Health Organisation

1. INTRODUCTION

[REDACTED]

[REDACTED]

[REDACTED]

The current study consists of 3 different groups:

- **Healthy subjects**
Group 1: 12 healthy subjects
- **Liver cirrhosis patients**
Group 2: 12 F4 Child-Turcotte-Pugh class A (Child-Pugh A) subjects (compensated)
Group 3: 6 F4 Child-Turcotte-Pugh class B (Child-Pugh B) subjects (decompensated)

The intention is to identify whether transporter activity in F4 liver cirrhosis patients on standard of care is similar or different from those in healthy subjects. The overall question this study will address, is how potential drug exposures may change, depending on their routes of metabolism and/or elimination from the body in F4 liver cirrhosis patients on standard of care compared to healthy subjects.

[REDACTED]

[REDACTED]

1.1 MEDICAL BACKGROUND

Based on the recommendations of the International Transporter Consortium's (ITC) white paper [[R10-1157](#)], regulatory agencies explicitly state drug transporters that should be investigated *in vitro* for inhibition by new investigational drugs during drug development. The specific transporters explicitly referred to by both the EMA guideline [[P15-06991](#)] and the FDA draft guidance [[R20-2271](#)] are the ATP-binding-cassette (ABC) transporter family, P-gp and BCRP, as well as the solute carrier (SLC) transporter family, OATP1B1, OATP1B3, OCT2, OAT1, and OAT3.

If *in vivo* inhibition of a drug transporter known to be relevant for drug disposition cannot be excluded based on *in vitro* data, an *in vivo* study is recommended by regulatory agencies. A valuable approach to investigate the activities of several different drug transporters in one single study is the “cocktail study”. This method, in which a mixture of well-characterized probe drugs is administered together with the new investigational product, is well established for investigation of cytochrome P450 (CYP450) mediated DDIs. Both the European Medicines Agency (EMA) and the Food and Drug Administration (FDA) recommend the use of cocktail studies also for investigating the activity of drug transporters [[P15-06991](#), [R20-2271](#)].

A cocktail of drug transporter substrates has been developed by BI during the last years. This cocktail consists of 0.25 mg digoxin (substrate of P-gp), 10 mg rosuvastatin (substrate of OATP1B1, OATP1B3 and BCRP), 10 mg metformin (substrate of OCT2, MATE1 and MATE2-K) and 1 mg furosemide (substrate of OAT1 and OAT3), thus covering all transporters of potential clinical relevance recommended by EMA and FDA (see above). In the given doses the cocktail demonstrated no mutual interactions [[R20-1915](#)].

1.2 DRUG PROFILE

1.2.1 Rosuvastatin

Rosuvastatin is a 3-hydroxy-3-methylglutaryl coenzyme A (HMG-CoA) reductase inhibitor indicated for treatment of hypercholesterolemia and for prophylaxis of cardiovascular events. Inhibition of HMG-CoA decreases hepatic cholesterol production which, in turn, stimulates hepatocellular uptake of low-density lipoproteins [[R22-4022](#)].

After oral administration, maximal rosuvastatin plasma concentrations are reached at ~ 5 h. Oral bioavailability is ~20 %, plasma protein binding is ~90 %, and V_Z/F is ~134 L. The liver is a principal compartment of distribution, with hepatocellular uptake being mediated mainly by OATP1B1 and, to a lesser degree, by OATP1B3. Elimination is mainly via faeces and to a lesser degree, via urine (principally via renal tubular secretion), with a t_{1/2} of 19 h [[R22-4022](#), [P14-07833](#)].

In therapy, the initial rosuvastatin dose is 5-10 mg once daily (q.d.), and during therapy, the daily dose may be increased to up to 40 mg [[R22-4022](#)].

Adverse reactions to rosuvastatin are normally mild and transient. Myalgia and myopathy with concomitant increase of creatine kinase, and, in rare cases, rhabdomyolysis have been observed during rosuvastatin therapy. Moreover, as for other HMG-CoA reductase inhibitors, a dose-dependent increase of liver transaminases may be observed [[R22-4022](#)].

Several drugs are known to influence the exposure of rosuvastatin. These drugs are forbidden in the study (antiviral drugs, ezetimibe and fibrates) In addition, subjects on the maximal dose (as per SmPC) of any statin would be excluded.

For a complete listing of adverse reactions, including frequency of occurrence, please refer to the current Summary of Product Characteristics (SmPC) [[R22-4022](#)].

1.2.2 Digoxin

The cardiac glycoside digoxin is a potent and specific inhibitor of the membrane-bound Na⁺/K⁺ ATPase. In cardiomyocytes, Na⁺/K⁺ ATPase inhibition increases intracellular Ca⁺⁺ concentrations during electromechanic coupling. Digoxin has positive inotropic and bathmotropic and negative chronotropic and dromotropic cardial effects. Use of digoxin is indicated in patients with tachyarrhythmia absoluta due to atrial fibrillation or flutter, with congestive heart failure due to systolic dysfunction, or with paroxysmal atrial fibrillation or flutter [[R22-4044](#)].

Digoxin oral bioavailability is ~60-80 %. Its volume of distribution is large at 510 L in healthy volunteers; plasma protein binding is ~20 %. Digoxin is eliminated principally (~80 %) by the kidney, with a t_{1/2} of approximately 40 h [[R22-4044](#)].

In therapy, digoxin is given first as a loading regime of up to 0.75 mg digoxin/day, followed by a maintenance regime controlled by therapeutic drug monitoring.

Adverse reactions to digoxin include cardiac arrhythmia, gastrointestinal complaints, and diverse symptoms of the central nervous system such as headache or psychiatric disorders.

Moreover, disturbances of colour vision may occur. In rare cases, gynecomastia, myasthenia, thrombocytopenia, hypersensitivity reactions or lupus erythematoses have been observed [R22-4044]. A complete listing of adverse reactions, including frequency of occurrence, may be found in the current SmPC.

Symptoms of digoxin toxicity include cardial, gastrointestinal, and central side effects. Moreover, hyperkalemia may occur in acute overdosing. Life-threatening intoxications were observed after doses of ≥ 10 mg digoxin [R22-4044].

In this study, digoxin will be used in single dose, lower than the dose used to achieve an immediate effect on the cardiovascular (CV) system. In patients with cirrhosis, no dose reduction is needed. Nevertheless, patients with relevant CV conditions are excluded from the study (see section 3.3.2). Many drugs may increase the effect of digoxin on the CV system. The use of low single dose is not expected to lead to severe CV effects in the participants in this study. The study drug furosemide is used in a very small dose, and it is not expected to have any influence the electrolytes which may increase the risk of CV effects of digoxin.

For a complete listing of adverse reactions please refer to the current SmPC [R22-4044].

1.2.3 Metformin

Metformin is an oral antidiabetic that reduces plasma glucose concentrations by decreasing intestinal glucose absorption and hepatic glucose production and by enhancing glucose utilization in peripheral tissues. Thus, metformin reduces basal (fasting) and postprandial plasma glucose in patients with type 2 diabetes mellitus (T2DM). However, metformin does not stimulate insulin secretion and is not causally related to hypoglycaemia in patients with T2DM or in healthy volunteers. Metformin is used in patients with T2DM if sufficient reduction of plasma glucose is not reached by diet and exercise alone [R22-4021].

After oral administration, t_{max} is reached at ~ 2.5 h, and oral bioavailability (of 500-850 mg) is ~ 50 -60 %. Plasma protein binding is negligible. However, metformin enters erythrocytes which probably compose a deep distribution compartment. CL_R of metformin is high (estimated population mean of 507 ± 129 mL/min) and the principal mode of elimination, with a $t_{1/2}$ of approximately 6.5 h [R22-4021, P11-01873].

The initial metformin dose is normally 500-850 mg up to three times daily. The dose may be increased to up to 3000 mg per day [R22-4021].

Most frequent adverse reactions to metformin are gastrointestinal complaints such as nausea, vomiting, diarrhoea, abdominal pain, or appetite loss. Moreover, metformin may cause changed taste (e.g., metallic taste), and very rarely or with unknown frequency, respectively, skin reactions or abnormal liver function tests. For a complete listing of adverse reactions, including frequency of occurrence, please refer to the current version of the SmPC [R22-4021]. In addition, metformin may, very rarely, cause lactic acidosis. This is a life-threatening disorder caused by metformin accumulation, principally in diabetic patients with severe renal insufficiency. In case of unspecific symptoms such as muscle cramps in combination with gastrointestinal disorder or severe asthenia, lactic acidosis needs to be considered. Other possible symptoms are dyspnoea, abdominal disorders, hypothermia, and coma [R22-4021]. To our knowledge, lactic acidosis has not been observed in healthy

volunteers, so far. High doses of up to 85 g metformin did not cause hypoglycaemia. However, lactic acidosis has been observed with this severe overdosing [[R22-4021](#)].

In this study, very low dose of 10 mg will be used. It is not expected that this dose will have significant clinical effect in the study participants.

For a more detailed description of metformin's profile please refer to the current SmPC [[R22-4021](#)].

1.2.4 Furosemide

Furosemide is a loop diuretic indicated for treatment of oedema (cardiac, hepatic, renal, or due to burns), arterial hypertension, oliguria, or pulmonary oedema. By inhibition of the $\text{Na}^+/\text{2Cl}^-/\text{K}^+$ carrier in the distal ascending limb of Henle's loop, furosemide increases diuresis and excretion of sodium, potassium, calcium, and magnesium [[R22-4020](#)].

After administration of furosemide as an oral solution, oral bioavailability is ~80 %. Maximal plasma concentrations (t_{max}) are observed at ~1 h. Plasma protein binding is 95 %, and V_z/F is 0.2 L/kg. Furosemide is eliminated principally as unchanged substance, to two thirds by the kidney (glomerular filtration and secretion) and to one third by excretion into bile [[R22-4020](#)]. In therapy, initial doses of oral furosemide are normally 40 mg, but higher doses of over 200 mg are possible in individual cases when diuresis with lower doses is not sufficient. Maintenance dose is normally 40-80 mg/day [[R22-4020](#)].

Adverse reactions include mainly electrolyte disorders including dehydration and hypovolemia, hearing disorders and allergic reactions including skin reactions. Symptoms of overdosing are characterized by excessive loss of electrolytes which may lead to hypotension, syncope, or delirium [[R22-4020](#)].

In this study, very low dose of 1 mg will be used. It is not expected that this dose will have significant clinical effect in the study participants.

For a complete listing of furosemide adverse reactions, including frequency of occurrence, please refer to the current SmPC [[R22-4020](#)].

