Statistical methods	The pharmacokinetics of each of the cocktail components rosuvastatin, digoxin, metformin and furosemide will be estimated in F4 liver cirrhosis patients compared to healthy subjects, based on the ratio (F4 liver cirrhosis patients to healthy subjects) of the geometric means (gMeans) of the primary endpoints. Additionally, their two-sided 90 % confidence intervals (CIs) will be provided. This method corresponds to the two one-sided t-tests procedure, each at the 5 % significance level. A difference of 2-fold or more, either increase or decrease, will be determined as being a clinically significant change. The statistical model will be an analysis of variance (ANOVA) on the logarithmic scale including effects for 'group', age, and BMI. CIs will be calculated based on the residual error from the ANOVA. Descriptive statistics will be calculated for all endpoints.

FLOW CHART

Visit	Day	Planned time (relative to drug administration) [hh:min]	Approximate clock time	Event and comment	blood sample for PK and biomarker analysis	Safety laboratory testing ^{a,b}	12-lead ECG	Vital signs (BP & PR) ^a	Physical examination	Urine collection for PK and biomarker analysis	Questioning for AEs and concomitant therapy ^c
1				Screening ¹							
2				Admission to trial site							
				Snack (optional)							
				F4 Liver cirrhosis patients take their morning medication ⁴							
				Baseline examinations							
				Standardised light breakfast ^{6,9,10}							
				Empty bladder ⁵							
				Administration of cocktail ^{8,9}							
				240 mL fluid intake ⁹							
				240 ml fluid intake ⁹ / lunch ¹⁰							
				Snack (optional) ⁹							
				Dinner ^{9,10}							
				Breakfast ¹⁰ (optional) and discharge from trial site							
3				Follow-up visit 1							
4				End of trial visit ¹¹							

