1.3 RATIONALE FOR PERFORMING THE TRIAL

The rationale for this study is to understand whether liver cirrhosis itself, along with standard of care, can result in a change in transporter activity of P-gp, OAT1, OAT3, OCT2, MATE1, MATE2-K, OATP1B1, OATP1B3 and BCRP in F4 liver cirrhosis patients compared to healthy subjects.

Liver cirrhosis is a longitudinal disease, going from F0 through to F4 compensated then decompensated. The current published data on NASH patients suggests that MRP2 is reduced due to it being mislocated, BCRP activity is increased and OATP1B3 activity is reduced. It is not clear whether this occurs in all stages of liver cirrhosis patients or only in the most severe stages of the disease [R22-3893, R22-3889, R22-3891]. Thus, the current study is to fill this information gap.

The intention is to identify whether the pharmacokinetics of a drug, based on transporter activity, is significantly different in F4 liver cirrhosis patients on standard of care compared to that observed in healthy subjects. The overall question this study will address, is how potential drug exposures may change, depending on their routes of metabolism and/or elimination from the body in F4 liver cirrhosis patients on standard of care compared to healthy subjects.

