2. TRIAL OBJECTIVES AND ENDPOINTS

2.1 MAIN OBJECTIVES, PRIMARY AND SECONDARY ENDPOINTS

2.1.1 Main objectives

The main trial objective, is to ascertain whether the transport activity of P-gp, OAT1, OAT3, OCT2, MATE1, MATE2-K, OATP1B1, OATP1B3 and BCRP, given by the C_{max} and AUC_{0-24} values for the different components in the transporter cocktail containing digoxin (P-gp) furosemide (OAT1 and OAT3), metformin (OCT2, MATE1 and MATE2-K) and rosuvastatin (OATP1B1, OATP1B3 and BCRP) are similar or different in F4 liver cirrhosis patients on standard therapy compared to healthy subjects.

This study will be conducted as an open label, single dose study, where PK samples will be assessed up to [REDACTED] postdose following dosing of the cocktail.

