2.3 PROPOSED FURTHER ENDPOINTS

If the data allows additional PK parameters not exclusive to those below, may also be calculated if required:

- AUC_{0-tz} (area under the concentration-time curve of the analyte in plasma over the time interval from 0 to the last quantifiable data point)
- $\%AUC_{tz-\infty}$ (the percentage of $AUC_{0-\infty}$ obtained by extrapolation)
- t_{max} (time from dosing to maximum measured concentration of the analyte in plasma)
- $AUC_{0-\infty}$ (area under the concentration-time curve of the analyte in plasma over the time interval from 0 extrapolated to infinity)
- λ_z (terminal rate constant in plasma)
- $t_{1/2}$ (terminal half-life of the analyte in plasma)
- AUC_{t1-t2} (area under the concentration-time curve of the analyte in plasma over the time interval t_1 to t_2)
- CL/F (apparent clearance of the analyte in the plasma after extravascular administration)

Proprietary confidential information © 2023 Boehringer Ingelheim International GmbH or one or more of its affiliated companies

- V_z/F (apparent volume of distribution during the terminal phase after extravascular administration)
- Ae_{t1-t2} (amount of analyte that is eliminated in urine from the time interval $t1$ to $t2$)
- Fe_{t1-t2} (fraction of given drug excreted unchanged in urine from time point $t1$ to $t2$)
- CLR_{t1-t2} (renal clearance of the analyte in plasma from the time point $t1$ to $t2$)

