7.1 NULL AND ALTERNATIVE HYPOTHESES

It is not planned to test any statistical hypotheses in a confirmatory sense.

The relative bioavailability of rosuvastatin, digoxin, metformin, and furosemide in compensated and decompensated F4 liver cirrhosis patients (Child-Pugh A and Child-Pugh B) compared with healthy subjects (reference) will be estimated by the ratios of the geometric means (test/reference) for all PK endpoints and their corresponding 2-sided 90 % confidence intervals (CIs) will be provided. This method corresponds to the two one-sided t-test procedure, each at the 5 % significance level. Since the focus is on estimation and not testing, a formal hypothesis test and associated acceptance range is not specified.

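### Furosemide plasma Cmax and AUC0-24 cannot alone support a statement on OAT1/OAT3 activity in cirrhosis, because one third of elimination is biliary; furosemide renal clearance should be a required endpoint for that statement

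*Protocol*

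**What the plan says.** Protocol 2.1.1 sets out to establish whether the activity of the listed transporters, "given by the C_{max} and AUC_{0-24} values for the different components in the transporter cocktail", differs between F4 cirrhosis patients and healthy subjects. Furosemide is the only component assigned to OAT1 and OAT3 (Protocol 1.1 and 2.1.1).

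Protocol 1.2.4 describes furosemide elimination as mainly unchanged drug, "to two thirds by the kidney (glomerular filtration and secretion) and to one third by excretion into bile", with 95 % plasma protein binding.

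The primary model (Protocol 7.2.2, SAP 7.4.1) has terms for group, age and BMI. It yields geometric mean ratios to healthy subjects with 90 % CIs. Sensitivity and supplementary analyses are marked not applicable. On how to judge a ratio, the synopsis says: "A difference of 2-fold or more, either increase or decrease, will be determined as being a clinically significant change". Protocol 7.1 says that "a formal hypothesis test and associated acceptance range is not specified".

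Urine is collected (5.3.1.2) and furosemide is assayed in it (5.3.2.2). Protocol 2.3 lists CLR, the "renal clearance of the analyte in plasma from the time point" t1 to t2, but only among parameters to be calculated if the data allow and if required. Section 7.2.4.1 makes further PK endpoints descriptive. Section 7.2.4.2, although headed for biomarkers, applies the 7.2.2 model to further PK endpoints.

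**The concern.** The OAT1/OAT3 reading belongs to the renal route. Plasma exposure reflects total clearance, renal plus biliary. The factor under study is liver disease, so the biliary share cannot be assumed equal in the groups being compared. A raised furosemide AUC ratio could then come from the liver, the kidney or both, and the primary analysis would not show which.

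The error can also run the other way: a rise in biliary clearance could hide a true renal fall and support a conclusion of similarity. What is at stake is the transporter conclusion in 2.1.1. The exposure estimate itself is unaffected.

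**Working it through.** The plan gives no sample size calculation, power or furosemide variability, so there is no figure of its own to reproduce.

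**Inputs from the documents.** Renal share 2/3 and biliary share 1/3 (Protocol 1.2.4). Groups of 12 healthy, 12 Child-Pugh A and 6 Child-Pugh B (Protocol 7.5). Two-sided 90 % CI (7.1).

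**Assumptions.** Linear kinetics; unchanged bioavailability and protein binding; AUC0-24 close to AUC0-∞. The bound below is for AUC and does not apply to Cmax.

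**Step 1, AUC ratio.** With r and b the fractional losses of renal and biliary clearance:

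AUC ratio = 1 / [2/3 × (1 − r) + 1/3 × (1 − b)]

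Check: complete renal loss (r = 1, b = 0) gives 1 / (1/3) = 3.0, in line with the roughly 3-fold rise with probenecid cited in Protocol 1.4.2.3.

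**Step 2, biliary loss with renal clearance intact (r = 0).** The last column is the renal loss that gives the same ratio with bile intact, (1 − 1/ratio) / (2/3).

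| Biliary loss | Relative clearance | AUC ratio | Equivalent renal loss |
|---|---|---|---|
| 25 % | 0.917 | 1.09 | 12.5 % |
| 50 % | 0.833 | 1.20 | 25 % |
| 75 % | 0.750 | 1.33 | 37.5 % |
| 100 % | 0.667 | 1.50 | 50 % |

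Renal clearance separates the two explanations. At an AUC ratio of 1.20 the CLR ratio is 1.00 if the cause is biliary and 0.75 if it is renal.

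**Step 3, the 2-fold criterion.** Biliary loss alone reaches at most 1.50. It does change the renal loss needed for a ratio of 2, which is r = [2/3 + 1/3 × (1 − b) − 1/2] / (2/3):
- bile intact: (1 − 1/2) / (2/3) = 75 %
- half the biliary route lost: (5/6 − 1/2) / (2/3) = 50 %
- all of it lost: (2/3 − 1/2) / (2/3) = 25 %

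**Step 4, masking.** A 50 % rise in biliary clearance with a 25 % fall in renal clearance gives 2/3 × 0.75 + 1/3 × 1.5 = 1.0, so the AUC ratio is 1.0.

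**Step 5, chance that the 90 % CI excludes 1.** Noncentral t with 30 − 3 − 2 = 25 df, pooled variance, SE = s × √(1/12 + 1/n) and s = √ln(1 + CV²). Covariate imbalance is ignored. The between-subject CV is an assumption, shown over a range.

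| Assumed CV | True ratio | Child-Pugh A (n = 12) | Child-Pugh B (n = 6) |
|---|---|---|---|
| 30 % | 1.5 | 95 % | 85 % |
| 50 % | 1.5 | 66 % | 51 % |
| 60 % | 1.5 | 54 % | 41 % |
| 30 % | 1.2 | 44 % | 33 % |
| 50 % | 1.2 | 24 % | 19 % |

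At a true ratio of 1.5, the chance that the point estimate reaches 2 is about 1 % (A) and 2.5 % (B) at CV 30 %, and about 7 % and 11 % at CV 50 %.

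**The case against.** The analysis reports exposure ratios, not transporter activity. SAP 7.4 describes the primary endpoint analysis as independent of the protocol's main objectives, and Protocol 7.1 puts the focus on estimation. The synopsis objective is worded in terms of Cmax and AUC. The overall question in Protocol 1.3 is how exposure changes according to route of elimination, and a biliary contribution is part of that answer. The separating data are already planned, and the public SAP is redacted where it covers further endpoints, so it may say more about CLR. All of this stands and limits the point to the inference in 2.1.1, which still equates exposure with transporter activity.

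Several stronger readings are tempting but not supported:

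- **Biliary impairment will be reported as an OAT change.** The documents give no size or direction for furosemide biliary excretion in cirrhosis. Protocol 1.3 does say "The current published data on NASH patients suggests that MRP2 is reduced due to it being mislocated", but it does not link MRP2 to furosemide, and the same sentence reports BCRP activity as increased.
- **Every furosemide ratio is ambiguous.** Under the stated assumptions, an AUC ratio above 1.5 cannot come from biliary loss alone.
- **The biliary share cancels in an inhibitor study.** It is constant there, but it still dilutes the ratio: halving renal clearance with bile intact gives 1.5, not 2.0.
- **A ratio of 1.5 can serve as a cut-off.** That needs unchanged bioavailability and binding, and it says nothing about Cmax.

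CLR is not a pure OAT measure either. It includes filtration, about 0.05 × GFR at 95 % binding. Total CLR also depends on the unbound fraction, and low albumin is one of the Child-Pugh criteria.

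**Conclusion.** The point holds as a gap in attribution. Furosemide Cmax and AUC0-24 are sound exposure endpoints, but the primary analysis cannot assign a difference in them to OAT1/OAT3. Under linear kinetics with unchanged bioavailability, binding and renal clearance, biliary loss could move the AUC ratio to anywhere between 1 and 1.50. That range corresponds to an apparent renal loss of 0 to 50 %.

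This alone would not meet the 2-fold criterion. It could give a CI that excludes 1, which matters because 7.1 sets no acceptance range, and it could lower the renal loss needed for a 2-fold call from 75 % to as little as 25 %. Whether any such biliary change occurs in these patients is not in the documents. A reader might infer that the furosemide result is biased; the documents show only that its cause would be unresolved. The change is worth making because it is cheap. The protocol also already treats renal clearance as the primary outcome for its renal-transporter biomarkers, NMN and m1A (2.3.1.2).

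**What to change.** 1. Keep furosemide Cmax and AUC0-24 as primary exposure endpoints.
2. In Protocol 2.3, make furosemide CLR a required endpoint. Analyse its ratio to healthy subjects with the 7.2.2 model, and reconcile 7.2.4.1 with 7.2.4.2 so that it is clear which further PK endpoints are modelled.
3. In Protocol 2.1.1 and SAP 7.4.1, state that a change in furosemide AUC or Cmax without a matching change in CLR is not by itself evidence of altered OAT1/OAT3 activity. Do not write in a fixed numerical cut-off.
4. Interpret CLR together with the protein-binding sample (Protocol 5.5) if furosemide is among the selected components. If it is not, state that limitation.

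Cost: wording in the protocol and SAP and one additional modelled endpoint. No new samples are needed, since urine is already collected and assayed for furosemide. The downside is that CLR depends on complete urine collection and may be less precise than AUC, which matters most with six Child-Pugh B patients.
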